6.2 Data Security

Only authorized study personnel will have access to study data, and access to identifiable data will be limited to staff who need the data to interact with participants. Survey and medical data will be in a separate database from identifiable data (e.g., name, address, etc.). The link between subject name and ID will be destroyed 6 years after the close of the study; other study data will be kept indefinitely. All computers used for research purposes adhere to the institution's requirements regarding password protection, data encryption, anti-virus protection, and intrusion detection. All Internet-based data communications will be encrypted. Physical records will be stored in a locked filing cabinet with the PI's locked office at each site. For participants who consent to be contacted for future studies (to be requested at the end of the final survey at 24 month follow-up), the study team will store their contact information (i.e., first and last names, phone number, email address) as well as cancer history (i.e.,

diagnosis, date of diagnosis, and end of treatment date) separately from research data on the PI's secure One Drive, with access granted only to the PI, study coordinator, and limited authorized research staff. We will store this information for up to 10 years from date of consent, after which it will be destroyed by the Primary Investigator.

6.3 Data and Safety Monitoring

A. Data/Safety Monitoring Plan

This is a minimal risk study. The PI and study staff at each site will continuously monitor for any potential adverse events (AEs). Anticipated adverse events include participant distress related to the intervention sessions or breach of confidentiality. Participant distress will be monitored in several ways. First, the study coordinator at each site will review patient reported distress on the baseline survey, which is generally completed in person at the same time as a routine medical visit. Individuals who report elevated distress (i.e., score >8 on 0-10 scale) will be assessed for safety, and if they express no intent to harm themselves, will be referred to clinical social work services. If there is concern about participant safety in the medical setting, the study will alert the treating clinical staff to initiate patient safety protocols and notify the site PI (licensed psychologist). If the participant is not at the medical center, research staff will coach them to go to their nearest emergency room for help and call 911 if needed. Second, interventionists will be trained to respond to patient distress at the time it occurs during intervention sessions, calling the Site PI (licensed psychologist) and referring to clinical social work services if needed. Third, study coordinators will review patient-reported distress as soon as possible following completion of all subsequent surveys, calling the patient to assess for safety as above if elevated distress occurs, making appropriate referrals, and documenting procedures. The online survey will also contain contact information for the study coordinator if patients have any questions or concerns while completing the survey. All staff will be trained to maintain confidentiality of patient data. Study staff will report any AEs immediately to the PI. [name] and the investigative team, in consultation with the Data and Safety Monitoring Board, will be responsible for evaluating each AE, determining whether it is study-related, and assessing any change to the risk/benefit ratio.

All unexpected and/or serious adverse events (AEs) occurring during the active portion of the intervention or up to 30 days after the last intervention session will be reported to the RBHS IRB in accordance with IRB policy. The research team will review and discuss via teleconference any serious adverse events to ensure protections to the participants and discuss any modifications to the protocol. If modifications are needed, they will be submitted immediately according to standard IRB procedures. The PI will also conduct a quarterly review of safety and adverse events to be discussed during monthly all-investigator calls.

B. Data/Safety Monitoring Board Details

The PI will convene a Data and Safety Monitoring Board (DSMB) composed of a biostatistician, a behavioral scientist, and a physician who are not associated with the study. The committee will be responsible for oversight of patient safety and will meet yearly to review patient safety and trial progress. This review will include for each arm of the study: the number of patients enrolled, withdrawals, serious adverse events both expected and unexpected, and responses observed. A report with recommendations from the DSMB will be submitted annually to the RBHS IRB with the continuing review for the study.

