- o Financial strain, a marker of socioeconomic status particularly relevant for young adults with cancer, will be measured using the Comprehensive Score for Financial Toxicity (COST),³⁴ an 11-item scale of financial toxicity associated with cancer treatment. Respondents rate each item on a 5-point Likert scale from 0 (*not at all*) to 4 (*very much*) in the past 7 days. The measure yields a total summary score, with higher scores indicating greater financial strain. It has demonstrated adequate internal reliability and face validity.³⁴ These items will be administered at baseline, 12 months, and 24 months. Given that young adults may demonstrate different levels of financial independence, those who indicate that they are not primarily responsible for paying for their medical care will respond to only two items regarding financial stress at baseline only. Those who indicate financial responsibility at baseline and everybody at 12 months, and 24 months follow-up, will respond to the full 11-item scale.
- Oncology Screening Tool, which is an adapted version of the NCCN Distress Thermometer and problem checklist to include problems specific to young adults. Participants first rate their distress on a 0-10 scale. Next, they are asked to check off areas of concern from the past week, including practical (e.g., housing arrangements, work, bills, transportation), family (e.g., parents, siblings, partner), emotional (e.g., sadness, isolation, guilt), social (e.g., isolation from friends, missing important events), physical (e.g., body image, sexual concerns, sleeping difficulty), and informational (e.g., understanding information, feeling involved in decision-making) needs. A total score from 0 to 51 is calculated. This checklist is used to prompt selection of problems to be addressed in the intervention for those assigned to receive the intervention.
- Demographic/Medical: Patients will report age, sex, independent living status, race, ethnicity, school/work status, health insurance coverage, marital status, whether he/she is a parent, and income. Potentially time-varying characteristics (i.e., school/work status, insurance status, income) will be repeatedly assessed at all follow-up surveys. Cancer diagnosis, date of diagnosis, and treatment received (e.g., chemotherapy, radiation, hematopoietic stem cell transplant), will be abstracted from the medical record by research staff. This information will be used to describe the sample and used as

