Participant distress will be systematically monitored in several ways. First, the study coordinator at each site will review patient reported distress on the baseline survey. Individuals who report elevated distress scores (i.e., ≥8 on 0-10 scale) will be assessed for safety, and if they express no intent to harm themselves, will be referred to clinical social work services. If there is concern about participant safety in the medical setting, the study will alert the treating clinical staff to initiate patient safety protocols and notify the site PI (licensed psychologist). If the participant is not at the medical center, research staff will coach them to go to their nearest emergency room for help and call 911 if needed. Second, interventionists will be trained to respond to patient distress at the time it occurs during intervention sessions, calling the Site PI (licensed psychologist) and referring to clinical social work services if needed. Third, study coordinators will review patient-reported distress at all subsequent surveys, intervening as above if elevated distress occurs and documenting procedures.

E. Minimizing Risks of Harm

Participants will be encouraged to contact the research team if they experience emotional discomfort or distress at any time during the study. All research staff will receive training to appropriately identify and handle instances when a patient would benefit from a referral (e.g., to a clinical social worker) for follow-up of emotional discomfort or distress.

To protect the confidentiality of participants, a series of security procedures will be undertaken. IRB and HIPAA regulations concerning confidentiality will be strictly enforced. All study personnel receive training and certification in human subjects protection and HIPAA regulations. Each study participant will be given a unique numeric identifier upon study entry. Names and other identifiable protected health information will not be stored in the same database as survey and

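### Sections 4.7 D and 6.3 A give different distress cutoffs (≥8 and >8) for the same safety assessment, so the protocol handles a score of exactly 8 in two ways

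*Combined protocol and SAP*

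**What the plan says.** The distress rating comes from the Oncology Screening Tool in section 1.9: "Participants first rate their distress on a 0-10 scale". Two sections then say what staff do with a high rating.

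- Section 4.7 D (Assessment of Social Behavior Considerations): "Individuals who report elevated distress scores (i.e., ≥8 on 0-10 scale) will be assessed for safety".
- Section 6.3 A (Data/Safety Monitoring Plan): "Individuals who report elevated distress (i.e., score >8 on 0-10 scale) will be assessed for safety".

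In both, the site study coordinator reviews the rating on the baseline survey. A participant above the cutoff who expresses no intent to self-harm is then referred to clinical social work. Both sections extend the rule beyond baseline. Section 4.7 D says "study coordinators will review patient-reported distress at all subsequent surveys, intervening as above if elevated distress occurs", and section 6.3 A has the coordinator "calling the patient to assess for safety as above if elevated distress occurs". Neither section refers to the other's cutoff.

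**The concern.** A trigger for a safety assessment should have one value. Here the inclusive cutoff is in the section on risks of harm and the exclusive one is in the section titled as the safety monitoring plan. A coordinator could reasonably work from 6.3 A alone. That coordinator would not be told to assess a participant scoring exactly 8, although 4.7 D requires it. Two sites could also treat the same score differently, each following a section of the current protocol.

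What is at stake is consistent safety follow-up of distressed participants. No estimate, test or error rate is involved.

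**Working it through.** There is no figure to reproduce, so the check sets the two sections side by side.

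| Element | Section 4.7 D | Section 6.3 A |
|---|---|---|
| Who reviews | Site study coordinator | Site study coordinator |
| What is reviewed | Distress rating on the baseline survey | Distress rating on the baseline survey |
| Cutoff on the 0-10 scale | ≥8 | >8 |
| Action | Safety assessment, then social work referral if no intent to self-harm | Same |
| Later surveys | Same rule carried forward | Same rule carried forward |

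**Step 1: is it one procedure or two?** Reviewer, input, action and referral all match, so a difference of purpose does not explain the two cutoffs.

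**Step 2: where do the rules differ?** Section 1.9 gives only the range of the scale, so whole-number ratings are an assumption. Under it:

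- ≥8 flags {8, 9, 10};
- >8 flags {9, 10};
- the difference is {8}.

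A finer scale would not widen the gap, since ≥8 and >8 separate only at the value 8.

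**Step 3: when does it apply?** Each section carries its own cutoff forward, so the discrepancy exists at baseline and at the 3, 6, 12 and 24 month surveys.

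**Step 4: can both sections be obeyed at once?** Yes. Assessing everyone at ≥8 meets 4.7 D and also covers everyone whom 6.3 A flags. Using >8 alone meets 6.3 A but falls short of 4.7 D at a score of 8.

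**Step 5: how many participants?** This cannot be computed. It needs the share of ratings equal to 8 and the cutoff that sites actually use, and the document gives neither.

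**The case against.** The strongest objection is that the whole point rests on one character. The text was read from PDF by a program, and a ≥ that lost its bar would read as >. The extraction has other character errors, such as NI/A for N/A in section 4.5. This cannot be excluded. Against it, ≥ came through correctly in 4.7 D, the two paragraphs are not word-for-word copies, and nothing in the text shows a misreading in 6.3 A. The point therefore stands on condition that the source is checked.

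A second objection is that the practical gap is narrow. Section 4.7 D applies throughout, and 6.3 A does not forbid assessing a score of 8. Staff review the protocol at start-up meetings (section 2.2), and weekly calls with site staff cover compliance (section 3.0). Other safeguards need no cutoff: ongoing adverse event monitoring, usual psychosocial care (section 2.3), referral training ("All research staff will receive training to appropriately identify and handle instances when a patient would benefit from a referral") and a route for participants to make contact ("The online survey will also contain contact information for the study coordinator"). Trainers also respond to distress during sessions. All of this lowers the residual risk. It does not give a coordinator a rule for a score of 8. The trainer safeguard covers only the intervention arm, and sessions are to be finished within 12 weeks (section 1.6 A), so it does not reach the 6, 12 and 24 month surveys.

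A reader might infer three stronger things, none of which the document supports:

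- **That 6.3 A holds the wrong symbol.** The text shows only that the sections differ. Preferring ≥8 is a protective choice and is not derived from the protocol.
- **That many assessments are at risk because the rule runs at five surveys.** Counting the surveys screened says nothing about how many ratings equal 8.
- **That participants scoring 8 have already been missed.** The protocol is written prospectively, and the supplied text gives neither enrolment status nor the cutoff in use.

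**Conclusion.** The inconsistency is real in the current text. One safety procedure has two cutoffs, at baseline and at all later surveys, with no statement of which governs. It affects only scores of exactly 8. The number of participants concerned is unknown and cannot be derived from the document. Power and the primary analysis are unaffected.

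The conclusion rests on two things: that the source PDF does read >8 in 6.3 A, which needs confirming, and that a rating of exactly 8 can be recorded, as it can with whole-number ratings. It is a minor correction, worth making because the character in question sets a safety threshold and is cheap to change.

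**What to change.** 1. Check section 6.3 A in the source PDF. If it reads ≥8, no change is needed.
2. If it reads >8, change it to ≥8. This is the more protective cutoff and satisfies both sections.
3. Put the same cutoff in the coordinator procedures and any automated survey alert, and tell the sites.
4. If data collection has begun, check that participants who scored exactly 8 were assessed, as 4.7 D requires.

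The cost is a one-symbol protocol modification, a notice to site staff and a few more safety calls, limited to scores of exactly 8.

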6.4 Reporting Results

A. Individual Subjects' Results

N/A – results will be calculated on the aggregate data; no relevant data for sharing with subjects.

B. Aggregate Results

We will post aggregate results on clinicaltrials.gov for public viewing.

C. Professional Reporting

It is expected that the results of this research will be submitted for publication in a timely manner following the conclusion of the study. The PI and all co-authors must review any abstract or manuscript prior to submission.

D. Clinical Trials Registration, Results Reporting and Consent Posting
This trial will be registered at clinicaltrials.gov. Results will be reported and the approved consent form uploaded.

6.5 Secondary Use of the Data

We will make de-identified data available for sharing with other qualified researchers for secondary research. This is described in the consent form.

7.0 Research Repositories - Specimens and/or Data

N/A

8.0 Approvals/Authorizations

Rutgers will serve as the IRB of record for this study. Reliance agreements with the IRBs of participating sights will be obtained prior to commencing the research.

